4. STUDY DESIGN AND PROCEDURES

4.1. Overall study design

The principles of the study are shown in **Figure 3**. The aim of the study is to investigate the effect of adding artificial loading to participants with obesity. The weights will be added via a weight vest consisting of 11 % (intervention or high load group) or 1 % (control or low load group) of the participants body weight at randomization; the vest will be worn for 5 weeks and 8 hours per day. Participants will be encouraged to be in a standing position for as many hours as possible of the vest wearing time and are required to be in a standing position at least 2 hours per day while wearing the weight vest. 25 participants will wear a heavy weight vest weighing 11 % of the participants body weight and 25 participants will wear a light weight vest weighing 1 % of the participants body weight. All participants will continue with their normal lifestyle.

Study code: ATLAS
Version No: 14.9

Date: 2021-02-01

[figure not shown]

Figure 3. Timeline for study. This figure shows the principles of the study. The dark green line illustrates two weeks before baseline including different measurements. The yellow line represents 2 weeks follow up period. The red line illustrates the intervention group, this group will wear a heavy weight vest with 11 % of body weight for 8 hours a day for 5 weeks. The dark blue line illustrates the control group, this group will wear a light weight vest with 1 % of body weight for 8 hours a day for 5 weeks. Both groups will be instructed to continue with their normal lifestyle during the intervention. The black line represents energy expenditure measurement with doubly labeled water (DLW) which will be performed on day -14 to 0 and on day 14 to 28. For detailed timeline of measurement with doubly labeled water see figure 4. The grey line represents registration of physical activity with accelerometers and a corresponding diary which will be performed on day -13 to -7 and on day 15 to 21. The orange line represents heart rate variability assessment from electrocardiography (ECG) registrations using 24-hour Holter monitoring which will be performed on day -13 and day 15. The purple line represents CT-scan of the abdomen performed on day 0 and day 35. The white line represents DXA-scan performed on day 0 and day 35. The light blue line represents Short Dietary Questionnaire (SDQ) to be registered before baseline and during intervention for evaluation of food intake the last fourteen days.

Blood drop symbol represents blood sampling. Performed on day -21, 0, 15, 35 and 49.

Water drop symbol represents intake of doubly labeled water. Performed in day -14 and 14.

Week -3 – Day -21 (Visit 1): Study center visit. Screening of potential participants. Information to the subject and collecting of written informed consent. Screening blood sampling. Measurements of body weight, height, blood pressure, and body composition.

Week -3 – Day -17 (Visit 2): Study center visit. Enrolled participants will receive information and material for the first day of the first DLW measurement.

Week -2 – Day -14 (Visit 3): Telephone visit. Participants will collect the first urine sample for the first DLW measurement at home and thereafter drink the first dose of DLW. This after an evening telephone visit from study personnel repeating the procedure protocol and explaining any uncertainties.

^{*} Telephone visit for participants. This to prevent mistakes, to document adverse advents and to minimize the loss to follow-up. Visits also to be performed in the evenings on the starting day of the doubly labeled water measurements to ensure compliance to protocol.

^{**} Physical visit for participants at study center.

Study code: ATLAS
Version No: 14.9

Date: 2021-02-01

Week -2 – Day -13 (Visit 4): Study center visit. Enrolled participants will receive equipment and information needed for first measurements with ECG and accelerometers. Collection of the second urine sample for the first DLW measurement. Obtainment of equipment and information needed for the first measurements with DLW. Measurements of body weight and body composition.

Week -1 - Day -7 (Visit 5): Telephone visit.

Week 0 – Day 0 (Visit 6): Study center visit. Fasting blood sampling, CT abdomen, DXA. Measurement of body weight, blood pressure, body composition. Collection of the last urine sample for the first DLW measurement. SDQ registration. Randomization and adding of weight vest. Obtainment of material and information for the first day of the second DLW measurement.

Week 1 - Day 7 (Visit 7): Telephone visit.

Week 2 – Day 14 (Visit 8): Telephone visit. Participants will collect the first urine sample for the second DLW measurement at home and thereafter drink the second dose of DLW. This after an evening telephone visit from study personnel repeating the procedure protocol and explaining any uncertainties.

Week 3 – Day 15 (Visit 9): Study center visit. Fasting blood sampling. Participants will receive equipment and information needed for second measurements with ECG and accelerometers. Collection of the second urine sample for the second DLW measurement. Obtainment of equipment and information needed for the second measurements with DLW. Measurements of body weight, body composition and waist circumference.

Week 3 - Day 21 (Visit 10): Telephone visit.

Week 4 – Day 28 (Visit 11): Study center visit. Collection of the last urine sample for the second DLW measurement. Measurements of body weight, waist circumference and body composition. SDQ registration.

Week 5 – Day 35 (Visit 12): Study center visit. Fasting blood sampling, CT abdomen, DXA. Measurements of body weight, waist circumference, blood pressure and body composition. Removal of weight west.

Week 7 – Day 49 (Visit 13): Study center visit. Fasting blood sampling. Measurements of body weight, blood pressure, body composition and waist circumference.

Study code: ATLAS
Version No: 14.9

Date: 2021-02-01

Doubly labeled water

[figure not shown]

Figure 4. Timeline for measurement with doubly labeled water. On day -14 a urinary sample will be collected as baseline measurement (sample 1). Thereafter the subject will consume a calculated dose of the isotope. Urinary samples will be collected in the morning and evening on day -13 (sample 2 and 3), morning and evening on day -6 (sample 4 and 5), evening of day -1 (sample 6) and morning of day 0 (sample 7). Sample 1, 2 and 7 will be collected at study center or at home.

Body weight, fat mass, water mass and fat free mass will be measured before intervention (day - 21, day -13, day 0), during the intervention (day 15, day 28) at the end of intervention (day 35) and at follow up (day 49) to determine the effect of added artificial weights on subjects with obesity.

Fasting blood sampling will be performed at the start of intervention (day 0), during the intervention (day 15), at the end of intervention (day 35) and at follow-up visit (day 49) to further determine the effects of adding artificial weights to obese individuals but also to elucidate the mechanism behind the "gravitostat". Blood glucose levels will be measured immediately. Blood samples, except blood glucose, will be analyzed either continuous or after all study subjects have been enrolled depending on human resources.

The study participants will report food intake before (day 0) and during (day 28) the intervention. This will be done using the validated questionnaire Short Dietary Questionnaire (SDQ) which will evaluate the food intake the last 2 weeks [13, 14].

Study subjects will be recruited by advertising in the local newspaper, on bulletin boards, social media, websites and with flyers. Potential study subjects will be informed about the hypothesis that people carrying a weight vest may lose body weight.

During the two weeks before baseline, measurements with doubly labeled water, ECG and accelerometers will be performed. The data collected during these two weeks will be used as baseline measurements.

Study code: **ATLAS** Version No: 14.9

Date: 2021-02-01

Procedures and flow chart 4.2.

Table 2 Study plan detailing the procedures each day

Table 2 . This table	summarizes	all the	procedures	conducted	within th	ne trial.

		Ta	able	2.	Th	is t	abl	e s	un	m	ariz	es	all	th	е р	roc	ed	ure	es (cor	ıdu	cte	ed v	with	nin	the	tri	al.		
	13	49	+/- 3 days		×			×			×		×	×	×	×	×			×										1
		35 – 49																												
Intervention ends	12	35	+/-2 days CT/DXA: +/-3 days		X			X		×	×		×	X	×	×	×			X	×	×								
		28 – 35																												
	11	28	+/-3 h		×			×		×			×	×	×								×			×		×		
		21-28																								×			×	
	10	21	+/-3 days	X				X		×														X	×	×				
		15-21																						X	×	×				
	6	15	See protocol		×			×		×	×		×	×	×	×	×			×				×	×	×	×	×		×
	8	14	See protocol	X				X		×																×			×	
		8 – 14																												
	7	7	+/- 3 days	X				×		×																				
		0-7																												
Interventionstarts	9	0	Study center: +/-3h CT/DXA: +/-3 days		Χ			Х		×	×		×	Х	×	×	×			Х	×	×	Χ			Х	×	×		
		-7 – 0																								×			×	
	2	L -	+/-3 days	×				×		×														×	×	×				
		-147																						×	×	×				
	4	-13	See protocol		×			×		×				×										X	×	×	×	×		×
	3	-14	+/- 3 days	×				×		×																×			×	
		-16 – -15																												
	2	-17	+/-3 days		X					X																	X			
		-2016																												
	1	-21			×				×	×	×	×		×	×			×	×	×										
	Visit	Timepoint (day)	Visting Window	Telephone visit	Study center visit		Study Procedures	Update Adverse events	Informed Consent	Information Study Procedures	Physical examination	Height for BMI	Wai≴ circumference	Body weight	Impedance	Fasting Blood Sample	Fasting Blood Glucose	Screening ECG	Screening Blood Sample	Blood pressure	DXA	CT abdomen	Reporting Food Intake (SDQ)	Reporting Physical Activity	Measurement with accelerometer	DLW measurment	Distribute DLW materials	Urine Sample at study center	Urine Sample at home	24 hour ECG

Study code: ATLAS

Version No: 14.9

Date: 2021-02-01

4.3. Rationale for study design

To avoid the risk of carry-over effects, we have decided to not use a crossover design. This could have decreased the variation of the measurement values and increased the power of the study. However, we believe there could be a risk of a carry-over effect with a cross over design. As this is a completely new effect in clinical studies, we have no information about the wash-out time needed to avoid this problem.

4.4. Study visits

4.4.1. Visit 0: Pre-screening

Potential and willing subjects that contact study investigators will in turn be contacted for a prescreening via a phone call. A brief introduction to the study will be given and information about the inclusion and exclusion criteria. Potential research subjects that are still interested in participating in the study will be booked for a physical screening visit with one of the study investigators.

4.4.2. Visit 1: Day -21 – Screening

Subjects that pass the pre-screening will be booked to a screening visit at the study center. Potential research subjects will receive both oral and written information about the study plan during the visit. They will have time to ask questions and discuss concerns with an investigator. A written informed consent will be obtained from subjects who want to participate in the study. To get enrolled the potential research subject need to meet all the inclusion criteria and must not meet any of the exclusion criteria. Potential subjects will receive an enrolment number at the screening visit obtained from the electronic Case Report Form. During the visit the subject will receive information about all upcoming visits and study procedures in oral and in written form. All subjects will receive a folder containing all study information needed. Visit 2 will be planned and scheduled.

Visit 2, 3 and 4 will be planned and scheduled.

During the visit the following examinations will be performed:

- Physical examination according to section 7.2.1.1 Physical examination.
- Blood pressure
- Body weight
- Fat mass, water mass and fat free mass will be measured using BIA
- Height measurement for BMI
- Screening blood sample to screen for common diseases that may distort the results and increase the risk of adverse effects. The substances will be measured according to section 7.1.2.6 Blood Samples.
- In fertile female participants human chorionic gonadotropin (hCG) will be measured according to the inclusion and exclusion criteria. hCG will be measured in urine according to section 7.2.1.3. Pregnancy.

All above examinations and samples need to be within normal range (or not clinically significant as judged by PI), according to inclusion and exclusion criteria, for a research subject to be included in the study. Subject will be reminded of the following study visit.

4.4.3. Visit 2: Day -17 – Distribution of DLW material

Visiting window: +/- 3 days.

Study code: **ATLAS** Clinical Study Protocol Version No: 14.9

2021-02-01 Date:

Study center visit. All willing subjects that are eligible according to the inclusion and exclusion criteria will be enrolled in the study. Any questions or uncertainties regarding study procedures will be clarified by study personnel. Any adverse advents will be documented.

Each subject will be thoroughly informed about the protocol for the doubly labeled water (DLW) measurements by study personnel. Subjects will then receive one container for collection of the first urine sample at home and a bottle containing a calculated dose of doubly labeled water. Further detailed written instructions on how to consume the prearranged dose of DLW and how to collect and store the urine sample will also be given.

Visit 3 and 4 will be planned and scheduled. The day before visit 3 subjects will receive a text message to their mobile phone with a reminder regarding visit 3 and the DLW measurements.

4.4.4. Visit 3: Day -14 - First DLW measurements

Visiting window: +/- 3 days.

Telephone visit that shall be performed in the afternoon or evening between 17:00 – 22:00 hours. Study personnel will call subjects and repeat the DLW procedure to be performed by the subjects later the same evening. It is crucial that subjects follow the protocol and they shall first be informed on how to collect the first urine sample (sample 1). Secondly, they shall be informed on how to consume the calculated dose of doubly labeled water for the first DLW measurement. The doubly labeled water should be consumed by the subject as the last consumption of the day. The subject will be reminded of visit 3 at the study center in the morning the following day.

4.4.5. Visit 4: Day -13 – Baseline measurements

Visiting window: Morning visit the day after visit 3.

Study center visit planned in the morning the day after visit 3. The second voiding of the day should be collected at the study center (sample 2) the morning after drinking the doubly labeled water dose. It is important that the first voiding of the day is not collected as sample 2. However, it is not as important if it is the second or third voiding of the day that is collected as sample 2. After sample 2 has been collected body weight shall be measured. Subjects will receive material for collection of urine sample 3-6 at home. Each subject will receive four containers for collection of urine samples and detailed oral and written instructions on how to collect and store the urine samples.

Subjects will receive an accelerometer for measurement of physical activity that will be worn on day -13 to -7. The accelerometer will be attached using a specially designed waist belt and the subject will be instructed how to reattach the device if so to be needed. The subject will be instructed to wear the accelerometer 24 hours per day for seven days. During the meeting a study nurse will attach a portable ECG monitor for a first 24-hour ECG recording. After attachment of the ECG monitor the subject is required to lay down for 1 hour to get a standardized registration, this shall be done at the study center. The subject will then carry the ECG for the following 23-hours during his/her usual activities. The subject will receive two pre-paid envelopes in which the ECG monitor and the accelerometer are to be returned after each registration is completed. Any changes to or new adverse advents will be documented.

During the visit the following examinations will be performed:

Body weight

Study code: ATLAS
Version No: 14.9

Date: 2021-02-01

Fat mass, water mass and fat free mass will be measured using BIA

During the visit on day -13 all future visits and study procedures will be planned and scheduled. The participant will receive dates and times for all upcoming visits in oral and written form.

First measurement with DLW and first ECG registration

Urinary samples will be stored by subject in a home freezer after collection. The containers for collection of urine should be dry and have an airtight lock. They should not be rinsed with water before collection of urine since this can disturb the analysis.

Day -14

- On the evening of day -14, before going to bed (usually between 22:00 and 24:00) the subject collects a voiding as a background sample (sample 1) at home.
- Afterwards the subject drinks the bottle with the calculated dose doubly labelled water
 as the last consumption of the day. The water is consumed straight from the bottle and
 afterward the bottle is filled with ~50 mL of tap water, closed with a screw cap and
 shaken, and subsequently the rinsing water is consumed as well.
- Procedures during this day are to be performed after a telephone visit from study personnel informing about the protocol

Day -13

- In the morning the second voiding of this day is collected (sample 2) and the body weight is thereafter measured. This step is to be performed at the study center.
- In the morning an ECG monitor will be attached and subjects are required to lay down to get a standardized registration. This shall be done at the study center.
- In the evening of this day another voiding is collected (sample 3) at home.

Day -6

- An early morning voiding is collected on day -6 (sample 4) at home.
- An evening voiding is collected on day -6 (sample 5) at home.

Day -1

An evening voiding is collected on day -1 (sample 6) at home.

Day 0

- An early morning voiding is collected on day 0 (sample 7) at the study center.

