5.2. Exclusion criteria

Subjects must not be included in the study if any of the following criteria are fulfilled:

 Chronic disease that could interfere with the participation in the study as judged by the investigator. For example poorly regulated type 1 or type 2 diabetes, cardiovascular disease that effect daily life, pulmonary disease that affects daily life, anemia or malignancy. Study code: ATLAS
Clinical Study Protocol Version No: 14.9
Date: 2021-02-01

2. Chronic pain such as pain that is constant and impairs quality of life as judged by the investigator; for example: significant back, hip and knee pain.

- 3. Regular consumption of medicine or natural supplements that affect weight, inhibit physical activity or increase the risk of adverse effects as judged by the investigator. The following drugs will not be accepted:
 - a. β-blockers, GLP-1-agonists, DPP-IV-inhibitors, SGLT2-inhibitors, sulfonylureas, insulin, orlistat, anti-obesity drugs, antidepressants, bisphosphonates, β2-agonists, oral corticosteroids, diuretics, benzodiazepines, or central nervous system stimulating drugs such as methylphenidate or dextroamphetamine.
 - b. Any illegal drugs according to local laws and regulation
- 4. Gastric by-pass surgery or equivalent metabolic surgery in the gastrointestinal tract.
- 5. Reduced mobility.
- 6. Pregnancy. Females of childbearing potential must confirm to use reliable contraception (intrauterine device, oral contraceptives or condom) and not suspect to be pregnant. Pregnancy test will be taken on all female subjects of fertile age unless permanently sterile, as judged by the investigator. Permanently sterile women can be excluded from the pregnancy test. Permanent sterilization methods include hysterectomy, bilateral salpingectomy and bilateral oophorectomy.
- 7. Change in body weight of 5 kg or greater during the past 3 months or recently started a strict diet. Also, a greater change in body weight than 3 kg difference between day -21 and day 0 will not be accepted.
- 8. Use of any illegal drugs according to local regulations or consuming excessive amounts of alcohol, tobacco, nicotine.
 - a. Excessive amounts of above-mentioned substances defined as:
 - Consumption of more than 9 glasses of wine for women, 14 glasses of wine for men (15 cl/glass 11 % alcohol) or equivalent as judged by the investigator during an ordinary week will not be accepted.

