9.2. Statistical analyses

9.2.1. Statistical methods

The primary endpoint of this randomized study will be the change in body weight at the end of the intervention (day 35) expressed as percent of original body weight at day 0, i.e. the day of the start of the intervention. The values will be calculated for all individuals participating in the study. The values will then be compared between the groups of individuals exposed of 11% and 1% of artificial loading, using ANCOVA (assuming normality).

- An analysis of covariance (ANCOVA) using age, BMI at the start of the study, sex, time per day wearing the west (hours/day), and percent of the vest bearing time standing up as covariates will be performed.
- Non-parametric analysis will be performed if data cannot be assumed normally distributed even after transformation.

The secondary endpoints of this study are found under section 3.2 in the study protocol. All the secondary endpoints are regarded as exploratory endpoints. A selection of the secondary endpoints includes change in:

- Body weight at day 15 and day 28 expressed as absolute (g) and relative (% of baseline value) change compared to baseline.
- Abdominal, visceral and subcutaneous fat at day 35 (end of intervention) expressed as absolute (g) and relative (% of baseline value) change compared to baseline.
- Fat free mass and fat mass at day 15, day 28 and day 35 expressed as absolute (g) and relative (% of baseline value) change compared to baseline.
- Energy expenditure during intervention (day 14-28) expressed as absolute (Joule per day) and relative (% of baseline value) change compared to baseline (day -14 to day 0).
- Physical activity during intervention (day 15-21) expressed as absolute (time distribution in a spectrum of physical activity intensities) and relative (% of baseline value) change compared to baseline (day -13 to -7).
- Waist circumference at day 15, day 28 and day 35 expressed as absolute (cm) and relative (% of baseline value) change compared to baseline (day 0).
- Heart rate variability (HRV) during intervention (day 15) expressed as absolute (frequency) and relative (% of baseline value) change compared to baseline.

Study code: ATLAS
Clinical Study Protocol Version No: 14.9
Date: 2021-02-01

- Serum concentration at day 15 and day 35 of circulating proteins, metabolites or electrolytes compared to baseline.

- Analysis at day 15 and day 35 of proteomics or metabolomics compared to baseline.

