These will be analyzed using the same methods as described for the primary endpoint. We will also compare absolute changes between the groups of individuals exposed to 11% and 1% artificial loading.

From the ANCOVA models adjusted for covariates, least square means (LSM) with 95 % confidence intervals will be calculated. P-values < 0.05 will be classified as significant. The p-values for within group comparison (5 weeks vs baseline) of the different parameters will be calculated using Wilcoxon signed rank-sum test.

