9.3. Sample size calculation

It is anticipated that a total of approximately 130 subjects are required to be screened to identify a statically significant (p<0.05) effect of 1.6% difference in relative body weight change between 5 weeks and baseline, when comparing high load with the low load group with 80% power. These calculations will allow a screening failure of 50% and a dropout rate of 20% after screening. Calculations are based on a standard deviation of 2% for change in body weight comparing 5 weeks with baseline. Power calculations demonstrate that a total of 25 evaluable participants per group are needed to significantly detect above mentioned effect size with a power of 80%.

Subjects will be screened and included in the clinical trial consequently until 25 subjects in the heavy weight vest group (intervention/high load group) and 25 subjects in the light weight vest group (control/low load group) are certain to complete the trial and be eligible for Full Analysis Set (FAS). Certainty will occur when that number of subjects have finished the intervention on day 35. Eligibility to Full Analysis Set (FAS) is defined as having completed the study visits on randomization (day 0) and at the end of intervention (day 35) and thus being eligible for assessment of the primary outcome. Screening and inclusion will probably be executed according to above mentioned calculations but could be adjusted along the timeline of the trial.

Study code: ATLAS
Version No: 14.9

Date: 2021-02-01

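### The primary ANCOVA omits the day -21 and day -13 weights already collected before randomisation; adding both as run-in changes would give a modest gain in precision at almost no cost.

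*Protocol*

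**What the plan says.** Section 4.1 of the protocol states "Body weight, fat mass, water mass and fat free mass will be measured before intervention" and names days -21, -13 and 0; section 7.1.1.1 repeats these days for body weight. The screening visit (4.4.2), the day -13 visit (4.4.5: "After sample 2 has been collected body weight shall be measured") and the randomisation visit (4.4.7) each include a weighing.

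Run-in weight is used once, for eligibility. Exclusion criterion 7 in section 5.2 reads "a greater change in body weight than 3 kg difference between day -21 and day 0 will not be accepted".

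The primary endpoint in section 9.2.1 is change at day 35 as a percentage of day 0 weight. The model is "An analysis of covariance (ANCOVA) using age, BMI at the start of the study, sex", followed by daily vest hours and the share of vest time spent standing. Stratification (6.1) is by age group and gender. Run-in weight or run-in change appears in none of these.

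**The concern.** The protocol treats pre-randomisation weight change as relevant, because it screens on it, but then does not use the measurements. The change between an earlier weight and day 0 carries two things that can predict the change from day 0 to day 35. One is a trend already under way. The other is the random error in the day 0 reading, which enters the endpoint with the opposite sign. What both predict stays in the residual. With 25 per arm, a chance difference between arms in run-in change also passes partly into the estimated vest effect. Starting BMI contains the day 0 weight but no trend, so it does little to remove either part.

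At stake is precision on the primary endpoint, in a trial whose power is close to its 80% target.

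**Working it through.** **1. The plan's own figure.** Section 9.3 gives an "effect of 1.6% difference in relative body weight change between 5 weeks and baseline" and says "Calculations are based on a standard deviation of 2% for change in body weight comparing 5 weeks with baseline". Section 9.2.1 adds "P-values < 0.05 will be classified as significant"; two-sided testing is assumed, since sidedness is not stated. Then n per group = 2 × (1.96 + 0.84)² × 2² / 1.6² = 24.5, rounded up to 25. This agrees with "a total of 25 evaluable participants per group are needed to significantly detect above mentioned effect size with a power of 80" percent. Power at 25 per group is 80.7% by the normal approximation and 79.1% by the exact t-test.

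**2. A model for the run-in weights.** The documents give no correlation, so a range is assumed. Let s be the SD of day-to-day noise in one weight (0.4, 0.6 or 0.8%), t the SD of personal drift per week (0, 0.1, 0.2 or 0.3%), and p the fraction of that drift that continues after day 0 (0, 0.5 or 1). The SD of the endpoint is held at the plan's 2%. Let x1 be the change from day -21 to day 0 (3 weeks), x2 the change from day -13 to day 0 (13/7 weeks), and y the change over the 5 weeks of intervention.

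- Var(x1) = 9t² + 2s²; Var(x2) = (13/7)²t² + 2s²; Cov(x1, x2) = 3(13/7)t² + s²
- Cov(x1, y) = 15pt² − s²; Cov(x2, y) = 5(13/7)pt² − s²
- R² for x1 alone = Cov(x1, y)² / [4 Var(x1)]; for both, R² = g′S⁻¹g / 4, where S is the covariance matrix of (x1, x2) and g their covariances with y

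The minus sign matters. Persistent drift makes the covariance positive and shared day 0 error makes it negative, so in x1 alone they can cancel.

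**3. One setting in full** (s = 0.6, t = 0.1, p = 0.5). Var(x1) = 0.81, Var(x2) = 0.7545, Cov(x1, x2) = 0.4157, g = (−0.285, −0.3136).

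- x1 alone: R² = 0.285² / (4 × 0.81) = 2.5%.
- Both: R² = (0.0613 − 0.0743 + 0.0797) / 0.4383 / 4 = 3.8%.

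**4. All 36 settings**, with power from the t-test at residual SD 2√(1 − R²):

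| Covariates | Median R² | Range in 34 of 36 settings | The other two |
|---|---|---|---|
| x1 only | about 3% | about 0-8% | 16%, 31% |
| x1 and x2 | about 4% | 0.4-11% | 16%, 31% |

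With both terms and two fewer degrees of freedom, power is about 79-83% in the 34 settings. The two exceptions have t = 0.3 and p = 1 with s of 0.6 or 0.4; power there is about 86% and 92%. The pair never explains less than x1 alone.

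**5. What starting BMI already removes.** In the same kind of model, with an assumed between-person spread of 4.3%, it explains at most about 1.3% of the variance, even with noise taken up to 1.0%.

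**6. Chance imbalance.** If run-in change has SD 1% (assumed), the difference in its mean between arms has SE 1.0 × √(2/25) = 0.28 points. The share that passes into the estimate is the slope of y on x1, (15pt² − s²) / (9t² + 2s²). At p = 0.5 it runs from −0.50 to +0.46, so a one-SE imbalance moves the estimate by at most about 0.28 × 0.50 = 0.14 points in either direction.

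**The case against.** Change from day 0 with randomisation at day 0 is a valid endpoint. Drift is balanced in expectation, and the confidence interval already allows for chance imbalance. The assumed SD of 2% for five-week change presumably already contains drift and day 0 fluctuation. On this view the point is a preference about an optional covariate. All three statements stand, and they limit the point to precision.

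A reader might go further and infer that the 3 kg allowance lets in drift larger than the 1.6% target. That comparison fails: 3 kg is a ceiling for one person, while 1.6% is a difference between group means. Other rules also limit drift: exclusion criterion 7 bars a change of 5 kg or more in three months and a recent strict diet, and criterion 9 bars drastic lifestyle change. A reader might also assume that run-in change simply carries on, so that an imbalance passes almost fully into the result. Much of run-in change is measurement noise, and the slopes in step 6 are smaller and often negative.

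The earlier weights are imperfect. An overnight fast is required at day 0 (4.4.7) but not stated for days -21 or -13 (4.4.2, 4.4.5), although section 7.1.1.1 standardises time of day and clothing. Visit windows let the interval from day -21 vary. This lowers the likely gain without making the covariates invalid.

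An unseen SAP could add covariates. The protocol, however, already names the list for its primary model, and the point concerns that list.

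**Conclusion.** The point holds as a low-severity improvement to the primary analysis. The plan collects two pre-randomisation weights that treatment cannot affect and leaves them out of a named covariate list. The likely gain is about 4% of variance explained, or one to two points of power; it could be close to nothing, and it is large only if drift is strong and fully persistent. These sizes rest on the assumed noise, drift and persistence, since the documents give none of them.

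The documents do not support a finding of bias or a claim that 25 per group is miscalculated.

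**What to change.** In section 9.2.1, pre-specify before outcome data are seen two further covariates in the primary ANCOVA: change in body weight from day -21 to day 0 and from day -13 to day 0, each in percent of day 0 weight. Entering the day -21, day -13 and day 0 weights separately would carry essentially the same information. Use both earlier weights, because a single day -21 to day 0 term is where drift and day 0 error cancel most easily.

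The cost is a line of text and two degrees of freedom: with 50 participants, an intercept, a group term and the five listed covariates, 43 residual degrees of freedom become 41. No new data are needed, and eligibility, visits and the endpoint stay as they are. The timing matters, because adding these terms after outcomes are known would look data-driven.

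A similar adjustment for the bioimpedance endpoints is optional, as section 9.2.1 calls all secondary endpoints exploratory. If it is made, first reconcile section 7.1.2.1, which omits day -13 from its measurement days, with sections 4.1 and 4.4.5, which include it.
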